2.5.2 Statistical hypothesis, model, and method of analysis

The following primary analysis will be tested as (Wang and Pocock, 2016):
H0: $\Psi \leq 1$ (win ratio ≤ 1) - The true number of 'winners' for sacubitril/valsartan is less than or equal to the true number of winners for enalapril.

H1: $\Psi > 1$ (win ratio > 1) - The true number of 'winners' for sacubitril/valsartan is larger than the true number of winners for enalapril.

The primary efficacy endpoint will be analyzed using the win ratio approach (Pocock et al 2012), with treatment as fixed-effect factor and stratified by country (Dong et al. 2017). Every patient in the sacubitril/valsartan arm will be compared to every patient in the enalapril arm within each stratum (country). All pairs will be compared first by time to CV death; if there is no winner, they will be compared for time to first HF hospitalization; if again there is no winner, they will be compared according to reduction in NT-proBNP levels between randomization and Week 12. If the comparison between changes in NT-proBNP levels does not result in a winner, the respective pairwise comparison is tied. When comparing the time to an event between two participants and at least one of the times is censored, the comparison is only performed up to the censoring time. The comparison of NT-proBNP is performed based on the relative change between randomization and Week 12 and takes into account that relative changes within $\pm 25\%$ are considered medically irrelevant; in detail, let x_{LCZ696} and x_{Enal} be the relative changes of participants in the sacubitril/valsartan and the enalapril arm, respectively. Then, a comparison of NT-proBNP is in favor of the subject in the sacubitril/valsartan arm if $x_{LCZ696} < 0.75 x_{Enal}$. On the other hand, the comparison is in favor of the subject in the enalapril arm if $x_{Enal} < 0.75 x_{LCZ696}$.

The win ratio is estimated by the ratio of the number of winners in the sacubitril/valsartan group and the number of winners in the enalapril group with weights defined as the reciprocal of the stratum (country) sample size.

$$\Psi = \frac{\sum_m^M w^{(m)} n_{LCZ696}^{(m)}}{\sum_m^M w^{(m)} n_{Enal}^{(m)}}$$

Where $n_{LCZ696}^{(m)}$ and $n_{Enal}^{(m)}$ are the total number of wins in the m^{th} stratum for the sacubitril/valsartan and Enalapril groups, respectively; $w^{(m)} = 1/N^{(m)}$ and $N^{(m)}$ is the total sample size in the m^{th} stratum.

The estimated win ratio and the corresponding two-sided 95% confidence interval will be provided. The overall type I error rate will be controlled at 2.5% (one-

sided). The contribution to the number of winners of each component of the composite endpoint will be reported. NT-proBNP at each visit and change from baseline will be summarized.

The summary will be presented by the treatment group for both the FAS and the PPS. The win ratio and its 95% confidence interval will be calculated using raw R code or the WINS package (version 1.4.3). The Appendix 4.1 presents the bootstrap algorithm description.

2.5.2.1 Time to CV death

The time from randomization to CV death will be considered as censored at the final analysis for participants who have not experienced a CV death. The censoring date for those participants without CV death prior to the analysis time point will be the following:

- date of death from non-CV causes, if the patient died.
- date of withdrawal of informed consent, if the patient withdrew the consent;
- date of last visit otherwise;

It will be considered as CV death for all the cases classified by the CEC as:

- Fatal Myocardial Infarction (MI);
- Heart Failure;
- Sudden Death;
- Fatal Stroke;
- Fatal Pulmonary Embolism;
- Cardiovascular Procedure-Related Death;
- Resuscitated Sudden Cardiac Arrest;
- All Undetermined causes of death (Presumed Cardiovascular Death, Presumed Sudden Death, Unknown death)

The definitions used to classify these events are described in detail in the CEC Charter, Version 1.0 – November 3rd, 2020. The classification frequencies for each cause will be presented descriptively.

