## 12.4 Analysis of the primary endpoint

### 12.4.1 Definition of primary endpoint

The primary endpoint is the hierarchically ordered composite consisting of time to CV death (worst category; earlier time to CV death is unfavorable), time to first HF hospitalization (second worst category; earlier time to HF hospitalization is unfavorable), and the relative change from Baseline to Week 12 in NT-proBNP levels (best category; more reduction or less increase are favorable) (Table 2-1). CV events will be confirmed by an independent Endpoint Adjudication Committee.

The effect is measured through the unmatched win ratio. The win ratio is based on pair-wise comparisons between participants receiving sacubitril/valsartan and participants receiving enalapril. A winner in the pair-wise comparison has a delayed time to the occurrence of CV death; if time to the occurrence of CV death is censored, a winner has a delayed time to the occurrence of first HF hospitalization event; if the times to both CV events are censored, a winner has a smaller change in NT-proBNP between Baseline and Week 12.

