Clinical Development

PARACHUTE: Prevention And Reduction of Adverse outcomes in Chagasic Heart failUre Trial Evaluation.

Clinical Study Protocol CLCZ696B3302

**A multicenter, prospective, randomized, open-label,
blinded-endpoint, Phase 4 study to evaluate the efficacy
and safety of sacubitril/valsartan compared with enalapril
on morbidity, mortality, and NT-proBNP change in patients
with chronic Chagas' cardiomyopathy**

Statistical Analysis Plan (SAP)

Document type: SAP Documentation

Document status: Version 2.1

Release date: 29-Apr-2025

Number of pages: 42

Property of Novartis
For business use only
May not be used, divulged, published or otherwise disclosed
without the consent of Novartis

Document History – Changes compared to previous final version of SAP

Version	Date	Changes
1.0	05/11/2020	First Version
2.0	09/04/2025	
• Section 2.6.1 and 2.6.2.4 - Recurrent events included as secondary endpoint.• Section 2.6.1 and 2.6.2.3 - Definition of days alive and out of hospital modified to within one year from randomization.• Section 2.8 - NT-ProBNP evaluation at month 8 included as an exploratory endpoint.• Section 2.5.2.1 - Definition of cardiovascular death included.
		
• Section 2.5.3 - Supplementary analysis for the primary outcome added to account for missing NT-ProBNP values and recurrent events.• Section 2.5.3 - Supplementary analysis for the primary outcome added to account for total death.• Section 2.8 - Exploratory analysis of the time-dependent interaction of SGLT2 inhibitors with treatment included.• Section 2.9 - Subgroup analysis comparing randomizations of COVID-19 during the pandemic period (and after)• Sections 2.5.1.1 and 2.5.1.2 - Estimands definitions
2.1	29/04/2025	
• Section 2.2 - Per protocol set definition updated.• Section 2.1.3 - Added imputation logic for partial missing dates• Section 2.4.1 - Calculation of drug adherence• Section 2.5.2 – Clarification of time to event censoring.• Section 2.9 - Subgroup analyses variables updated

Table of contents

	Table of contents	3
	List of abbreviations	5
1	Introduction	6
1.1	Study design.....	6
1.2	Study objectives and endpoints	8
2	Statistical methods.....	9
2.1	Data analysis general information	9
2.1.1	General definitions	10
2.1.2	Randomization	12
2.1.3	Partial information for dates.....	12
2.2	Analysis sets	13

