2.6 Analysis of secondary efficacy objectives

2.6.1 Secondary endpoints

The secondary efficacy endpoints besides the primary decomposition as described above are:

1. Time from randomization to the occurrence of the first HF hospitalization or CV death;
2. Time from randomization to all-cause mortality.
3. Time from randomization to sudden death or resuscitated sudden cardiac arrest.
4. Number of visits to an ER due to HF that needs intravenous drugs.
5. Number of days alive out of the hospital within 1 year from randomization.
6. Recurrent events: number of HF hospitalizations and CV deaths.

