4.1 PARACHUTE-HF Win Ratio bootstrap algorithm

1. The **win_ratio()** function determines the winner in each match between Enalapril and Sacubitril/Valsartan patients based on a hierarchical evaluation. The **win_ratio** function will be used in the pairs of patients from both groups within each stratum.
 - If the Sacubitril patient dies, and their follow-up time is shorter (regardless of whether the other patient dies), Enalapril wins. Conversely, if the Enalapril patient dies and their follow-up time is shorter, Sacubitril wins. Otherwise, it is a tie.
 - If the participants tied using previous comparison then a comparison in time to first HF hospitalization is performed: if the Sacubitril patient is hospitalized for heart failure (HF) and the time to first hospitalization is shorter than that of the Enalapril patient (or shorter than their total follow-up time if they were hospitalized for HF), Enalapril wins. The same logic applies in reverse for Sacubitril. Otherwise, it is a tie.
 - If the participants tied using previous comparison then a comparison in NT-ProBNP changes within 12 weeks is performed: The **NT_ProBNP_relative_change** endpoint is defined as the ratio: **NT-ProBNP at Week 12 / NT-ProBNP at Baseline**. The match outcome is determined as follows:
 - If $\text{NT_ProBNP_change_Sacubitril} < 0.75 \times \text{NT_ProBNP_change_Enalapril}$, Sacubitril wins.
 - If $\text{NT_ProBNP_change_Enalapril} < 0.75 \times \text{NT_ProBNP_change_Sacubitril}$, Enalapril wins.
 - Otherwise, it is a tie.
2. **Matrix W** contains the weight assigned to each country, calculated as $1/N_i$, where N_i represents the number of patients per stratum i , with i belonging to {Argentina, Brazil, Colombia, Mexico}.
3. **resultados_wr(BR)** is a data frame containing match results for Sacubitril vs. Enalapril patients in **Brazil**, computed using the **win_ratio()** function. Similar datasets (**resultados_wr(AR)**, **resultados_wr(CO)**, **resultados_wr(MX)**) are created for the remaining strata.
4. **resultados_wr** compiles all match results into a single data frame.

5. Calculates the total number of wins for each group and the number of ties per stratum and overall. In each stratum, the observed **Win Ratio (WR)** is calculated as the number of Sacubitril wins divided by the number of Enalapril wins.
6. The **Dong's Win Ratio** is then computed using the weights from **W** and the number of wins in each stratum:

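### SAP 2.5.2.1 lists resuscitated sudden cardiac arrest as CV death without requiring that the participant died, which conflicts with the protocol's first tier and with SAP Appendix 4.1

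*SAP*

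**What the plan says.** SAP 2.5.2.1 introduces its list with "It will be considered as CV death for all the cases classified by the CEC as". The list includes "Resuscitated Sudden Cardiac Arrest". The myocardial infarction, stroke and pulmonary embolism entries are marked as fatal, and the procedure-related entry is worded as a death. The arrest entry has no such marker.

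The same section places the class definitions elsewhere: "The definitions used to classify these events are described in detail in the CEC Charter, Version 1.0". It also promises a breakdown: "The classification frequencies for each cause will be presented descriptively".

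Other parts of the plan treat death and resuscitated arrest as different things:

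- Protocol 12.4.1 defines tier 1 by CV death alone: "A winner in the pair-wise comparison has a delayed time to the occurrence of CV death".
- SAP 2.6.1 keeps a separate secondary endpoint 3, "Time from randomization to sudden death or resuscitated sudden cardiac arrest". Protocol Table 2-1 has the same endpoint.
- SAP Appendix 4.1 starts tier 1 with a death: "If the Sacubitril patient dies, and their follow-up time is shorter (regardless of whether the other patient dies), Enalapril wins".

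The SAP document history records for version 2.0 only "Definition of cardiovascular death included". SAP section 3, on changes to protocol-specified analyses, does not mention it.

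**The concern.** A resuscitated participant is, on the ordinary meaning of the word, alive. If the list is programmed as written, that participant receives a CV-death date at the arrest and loses the tier-1 comparison to someone in the other arm who really died later.

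The same definition would carry into:

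- the CV-death Cox model and Kaplan-Meier curves (SAP 2.5.3);
- the composite of HF hospitalization or CV death (secondary endpoint 1);
- the recurrent-event analyses, where the joint frailty model would treat a survivor's arrest as terminal;
- possibly the count towards 302 events. No section says which definition that trigger uses, and a survivor adds to it only without an earlier HF hospitalization.

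The estimands would also stop being nested. The supplementary estimand (SAP 2.5.1.2) replaces CV death with death from any cause, which should contain CV death. Under the literal reading it does not.

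**Working it through.** **1. The texts side by side**

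| Place | What makes a tier-1 event | Does a survived arrest count? |
|---|---|---|
| Protocol 12.4.1 | CV death | No |
| SAP 2.5.2.1 | Any case in a listed CEC class | Yes, if read literally |
| SAP Appendix 4.1 | The patient dies | No |
| Protocol Table 2-1 and SAP 2.6.1, secondary endpoint 3 | Not tier 1; sudden death or resuscitated arrest | Counted here as its own component |

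Appendix 4.1 does not define dying and does not say CV, so a programmer must go back to 2.5.2.1 for the definition. The two SAP sections therefore cannot both be followed for a survivor.

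**2. The plan's own figure**

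Inputs from Protocol 12.8.1 and 6.1.3: annual rates 0.20 (enalapril) and 0.16 (sacubitril/valsartan), follow-up uniform from 1.5 to 3 years, 450 per arm, no loss to follow-up. For an exponential hazard L, expected events per arm = 450 × [1 − (e^(−1.5L) − e^(−3L)) / (1.5L)].

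- L = 0.20: 450 × [1 − (0.7408 − 0.5488)/0.30] = 162.0
- L = 0.16: 450 × [1 − (0.7866 − 0.6188)/0.24] = 135.3
- Sum 297.3 against the stated 302 (−1.6%). The planning inputs reproduce, although this does not test the point itself.

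**3. True CV deaths to expect**

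The protocol puts 66% of first events as HF hospitalizations, so 34% are CV deaths: hazards 0.34 × 0.20 = 0.068 and 0.34 × 0.16 = 0.0544. Assuming that risk is unchanged after an HF hospitalization, the same formula gives 63.7 + 51.7 = 115.4.

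**4. What the literal reading would do**

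The documents give no arrest frequency, so the rates below are assumptions. Each row is 300 simulated trials of 450 per arm, unstratified, with a Week 12 NT-proBNP ratio of 0.75 and a log-scale SD of 0.7 (assumed; the plan states none). Each trial was analysed with and without survived arrests counted as CV deaths.

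| Arrests per 100 patient-years (enalapril) | Treatment HR on arrests | Added CV deaths | Win ratio | CV-death rate ratio |
|---|---|---|---|---|
| 0.2 | 1.25 | 4 | 1.450 to 1.442 | 0.827 to 0.839 |
| 0.5 | 1.25 | 10 | 1.450 to 1.431 | 0.793 to 0.824 |
| 1 | 0.80 | 15 | 1.463 to 1.452 | 0.801 to 0.805 |
| 1 | 1.00 | 18 | 1.456 to 1.433 | 0.805 to 0.830 |
| 1 | 1.25 | 20 | 1.459 to 1.419 | 0.789 to 0.846 |
| 2 | 0.80 | 31 | 1.443 to 1.428 | 0.797 to 0.798 |
| 2 | 1.00 | 34 | 1.457 to 1.411 | 0.797 to 0.850 |
| 2 | 1.25 | 38 | 1.457 to 1.387 | 0.795 to 0.890 |

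In the last row the share of trials with a significant win ratio barely moves (99.7% to 98.7%). The joint criterion used in the sample-size section (significant win ratio and both component hazard ratios below 1) falls from 82% to 69%, because the CV-death ratio exceeds 1 more often. Monte Carlo error on a single power figure is about 2 points. With no survivors, nothing changes.

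**The case against.** The strongest reply is that the list is a list of causes of death.

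- Its Heart Failure entry also lacks the word fatal. Read as literally as the arrest entry, every HF case classified by the CEC would be a CV death and tier 2 would collapse into tier 1, which cannot be intended.
- The final entry speaks of causes of death, and the next paragraph refers to causes.
- On that reading the arrest class holds people who were resuscitated and then died, and Appendix 4.1 agrees. The charter that defines the classes is not among the documents.

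This stands as a plausible reading. A reader might infer that living participants do enter the top tier as dead and that every CV-death result is therefore wrong. The documents do not support that: they show an ambiguous rule, not how it will be applied. The reply also shows that simply deleting the line could remove genuine deaths that followed an initial resuscitation.

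On size, the only relevant treatment effect in the documents is the 22% reduction in resuscitated and non-resuscitated sudden death cited in Protocol 8.5.2. Take 27 arrests (3% of 900, assumed) split in the ratio 0.78: 15.17 and 11.83. The ratio of CV-death counts moves only from 51.73/63.67 = 0.812 to (51.73 + 11.83)/(63.67 + 15.17) = 0.806. A reader might also suppose that survived arrest is frequent here. The protocol describes frequent ventricular arrhythmia, not survived arrest.

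Finally, reporting by class would expose any survivors, and neither all-cause mortality nor the all-cause-death win ratio depends on this list. That helps detection, but it does not correct the primary analysis. Nor does the cause-of-death reading remove the need to say so in the SAP.

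**Conclusion.** The point holds as a conflict to be reconciled before database lock. As worded, SAP 2.5.2.1 lets a survivor count as a CV death. Protocol 12.4.1, secondary endpoint 3 and Appendix 4.1 all say otherwise, and section 3 does not declare a change. Whether any survivor would be so counted cannot be settled without the CEC Charter.

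The effect depends on a number the documents do not give. It is nil with no surviving cases. Up to about 1 arrest per 100 patient-years the win ratio moves by at most about 0.04. The CV-death rate ratio moves materially near 2 per 100, from 0.80 to 0.85 with no treatment effect on arrests and to 0.89 with an adverse one (HR 1.25). At 1 per 100 only the adverse case moves it by as much as 0.06. If arrests share the planned HR of 0.80, the CV-death ratio hardly moves at any rate tried. These figures rest on assumed arrest rates, an assumed NT-proBNP SD, constant hazards and an unstratified analysis.

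**What to change.** In SAP 2.5.2.1, restrict the list to participants who actually died, for example by rewording the entry as death following resuscitated sudden cardiac arrest, and give the Heart Failure entry the same qualifier. State that the event date is the date of the actual death, and that survived arrests count only in secondary endpoint 3. Make Appendix 4.1 point to this definition and say CV death. Check the wording against the CEC Charter and confirm the 302-event count on the same definition.

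If the sponsor does intend survivors to count, the tier should be renamed as a composite of CV death or resuscitated arrest, the event date specified, the change declared in SAP section 3, and a deaths-only sensitivity analysis added.

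The cost is a line or two of SAP text and a check of the derivation before lock. The downside is possibly a few fewer events towards 302.

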2.5.2.2 Time to first HF hospitalization

The time from randomization to first HF hospitalization will be considered as censored at the final analysis for participants who have not experienced a HF hospitalization. The censoring date for those participants without a HF hospitalization prior to the analysis time point will be the following:

- date of death, if the patient died.
- date of withdrawal of informed consent, if the patient withdrew the consent;
- date of last visit otherwise

2.5.2.3 NT-proBNP measurement

Cardiovascular death and HF hospitalization are at a higher hierarchy level than NT-proBNP in the composite primary endpoint for win ratio analysis. Therefore, missing values due to CV death or after hospitalization due to HF do not affect the analysis. Missing NT-proBNP measurement at Week 12 due to other reasons (e.g., non-CV death) are expected to be infrequent; they may result in more ties with minimal impact on the power. Therefore, no imputation will be made for missing NT-proBNP measurement at Week 12 for primary analysis, any match against a participant without NT-proBNP measurement will be considered a tie.

Baseline NT-ProBNP values may be unavailable for some samples. In such cases, if participants provided a local NT-ProBNP sample during screening phase, those values will be imputed for primary evaluation. Exams results disposed as > or < then any value, will be considered as exactly the limit value.

2.5.3 Supportive analyses

In addition to the primary analysis, the primary efficacy endpoint will be supportively analyzed for the PPS using the same primary analysis model.

Additionally, a supplementary analysis will be performed using the same statistics described for the primary efficacy endpoint, using total hospitalizations for HF instead of time to first HF hospitalization, if participants tied in number of hospitalizations, the winner will be the one that had the first event later. All other cases where the NT-proBNP values are missing for baseline or W12 will be treated as a tie in NT-proBNP for every match also tied for both the previous hierarchical endpoints.

Additional analyses will be performed on each individual component of the primary endpoint that occurs during the Randomized Treatment Epoch of the study to quantify the strength of the effect of each component.

For CV death and first HF hospitalization:

- Cox's proportional hazard model will be used to analyze time to CV death, and time to first HF hospitalization, respectively, with treatment as fixed-effect factor and stratified by country performed for both the FAS and the PPS; Hazard Ratios with 95% confidence intervals will be presented,
- The survival function for each treatment arm will be estimated by the Kaplan-Meier method presenting curves for each treatment arm for both the FAS and PPS.

For NT-proBNP:

- ANCOVA model will be used to analyze relative changes of NT-proBNP from baseline to Week 12 with treatment and country as fixed-effect factors and baseline NT-proBNP as covariate. Results will be presented as mean differences in relative change with 95% confidence intervals.
- A supplementary analysis will be performed for the absolute value of NT-proBNP using the same model and covariates. If the assumptions of normality and homoscedasticity are rejected based on graphical verification, a generalized linear model with a different distribution, such as Gamma, Log-

Normal, or Inverse-Gaussian, will be tested. The model with the best likelihood function will be chosen, and results will be presented as a mean ratio with 95% confidence intervals.

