#### **12.4.3.2 Time to first HF hospitalization**

The time from randomization to first HF hospitalization will be considered as censored at the final analysis for participants who have not experienced a HF hospitalization and for whom at least one of the following applies at or prior to the analysis time point:

- withdrawal of informed consent
- loss to follow up
- cardiovascular death
- death from non-CV causes

The censoring date for those participants without a HF hospitalization prior to the analysis time point will be whichever occurs first of the following:

- date of withdrawal of informed consent
- date of last visit (Visit 199)
- date of death from CV cause
- date of death from non-CV causes

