#### **12.4.4 Sensitivity and supportive analyses**

##### **Supportive analyses**

In addition to the primary analysis, the primary efficacy endpoint will be supportively analyzed for the PPS by means of the same primary analysis model.

Additional analyses will be performed on each individual component of the primary endpoint that occurs during the Randomized Treatment Epoch of the study to quantify the strength of the effect of each component.

For CV death and first HF hospitalization:

- Cox's proportional hazard model will be used to analyze time to CV death, and time to first HF hospitalization, respectively, with treatment as fixed-effect factor and stratified by country
- a log-rank test will be performed for both the FAS and the PPS
- the survival function for each treatment arm will be estimated by the Kaplan-Meier method presenting curves for each treatment arm for both the FAS and the PPS

For NT-proBNP:

An ANCOVA model will be used to analyze the change of NT-proBNP from Baseline to Week 12, with treatment and country as fixed-effect factors and baseline NT-proBNP as covariate.

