2.6.2 Statistical hypothesis, model, and method of analysis

2.6.2.1 Analysis of time to events endpoints

The time from randomization to

- the first composite event of CV death or HF hospitalization,
- all-cause mortality, and
- to sudden death or resuscitated sudden cardiac arrest

will be analyzed using Cox's proportional hazards model with treatment as fixed-effect factor and stratified by country. The estimated hazards ratio and the corresponding 2-sided confidence interval will be provided for the FAS.

The Kaplan-Meier curves by treatment arm will be presented for the FAS. Additionally, the frequency and percentage of patients with a composite CV event will be provided by treatment arm.

Proportional hazard assumptions will be tested by weighted residuals diagnostics and by visual inspection. Alternative parametric survival models (Exponential, or Weibull, or Log-logistic, or log-normal survival models) will be used if

the risk proportional assumption did not meet. The model with the best likelihood function will be chosen in that case.

2.6.2.2 Analysis of number of visits to an ER due to HF that needs intravenous drugs

The rate of visits to an ER due to HF that needs intravenous drugs will be analyzed using a generalized linear model assuming a negative binomial distribution. The time at risk for a subject is the length of follow-up. The analysis model will include terms for treatment and country as fixed-effect factors and log (follow-up duration) as the offset. An estimate of the ratio of event rates between the treatment arms, together with the 95% confidence interval, will be presented for the FAS.

The number of visits to an ER due to HF that needs intravenous drugs during the treatment period will be summarized by treatment arms.

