2.11 Sample size calculation

An analysis of the 55 patients with Chagas' disease in the enalapril group in PARADIGM (Ramires et al 2018) showed an event rate of 20 events per 100 subject-years for CV death plus hospitalization due to HF. Similar event rates, for CV death plus hospitalization due to HF in CCC patients, has also been seen in the BENEFIT and SHIFT studies. Therefore, we assumed a rate of approximately 20 events per 100 subject-years for the CV event (composite of CV death and first HF hospitalization) for the enalapril group. Approximately 66% of the first CV events are HF hospitalizations. For the sample size calculation, we assumed a rate of 16 events per 100 subject-years for the sacubitril/valsartan group, which corresponds to an effect of 20%.

The sample size was determined based on a simulation study under the assumptions of:

- a one-sided type I error rate of 2.5%,
- a target power of 85%,
- a uniform accrual of 18 months,
- a study duration of 36 months, i.e. the individual follow-up times varied between 18 and 36 months,
- an annualized event rate of 0.16 for the composite of CV death or first HF hospitalization in the sacubitril/valsartan group, and an annualized event rate of 0.20 for the composite of CV death or first HF hospitalization in the enalapril group,
- a relative change of NT-proBNP between week 12 and baseline that is 25% lower in the sacubitril/valsartan group compared to the enalapril group

During the simulation study, a simulated trial was considered to show superiority of sacubitril/valsartan over enalapril when the win ratio was significantly larger than one based on the one-sided significance level of 2.5%, and the estimated hazard ratio of sacubitril/valsartan versus enalapril for time to first HF hospitalization was less than one, and the estimated hazard ratio of sacubitril/valsartan versus enalapril for CV death was less than one.

Based on these assumptions and criteria for superiority, a study with 900 patients results in the target power of 85%. Moreover, 302 participants with events for the composite of CV death or first HF hospitalization can be expected in the study.

As the primary hierarchical composite endpoint is evaluable as long as subject experience either a HF hospitalization, CV death, or have a NT-proBNP value measured at Week 12, the sample size calculation did not assume any loss of follow-up.

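### First HF hospitalisation is censored at death and shown by Kaplan-Meier, so the arm-level curves overstate its cumulative incidence, by 1.4 points (0.68 SE) at 24 months and 2.1 points (0.84 SE) at 30 months in the enalapril arm at the plan's rates

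*SAP*

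**What the plan says.** For participants without an HF hospitalisation, SAP 2.5.2.2 sets the censoring date first as "date of death, if the patient died", whatever the cause. Protocol 12.4.3.2 lists the two kinds of death separately, one of them as "date of death from CV cause".

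The display follows in SAP 2.5.3, for CV death and for first HF hospitalisation, in both the FAS and the PPS: the survival function "will be estimated by the Kaplan-Meier method presenting curves for each treatment arm". Protocol 12.4.4 has the same instruction: "the survival function for each treatment arm will be estimated by the Kaplan-Meier method presenting curves for each treatment arm".

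SAP 2.6.2.5 carries the censoring rules of 2.5.2.1 and 2.5.2.2 over to the secondary endpoints. For those, which include sudden death or resuscitated arrest, SAP 2.6.2.1 says: "The Kaplan-Meier curves by treatment arm will be presented for the FAS". In SAP 2.5.2.1, CV death is censored at non-CV death.

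Neither document plans a cumulative incidence function or any other estimator of absolute risk that accounts for competing events.

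**The concern.** Kaplan-Meier treats a censored participant as still able to have the event later. That is reasonable for someone who reaches the end of the study, but not for someone who has died. With death censored, one minus Kaplan-Meier refers to a setting in which nobody dies before hospitalisation, and even that reading needs death and hospitalisation to be independent. It does not estimate the share of participants hospitalised by a given time.

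Death is not a rare competing event here. The planning section states: "Approximately 66% of the first CV events are HF hospitalizations". The remaining 34% of first CV events are therefore CV deaths.

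SAP 2.5.3 describes these component analyses as a way of showing how strong the effect is on each part of the primary endpoint, so readers can be expected to take absolute risks from the curves. Both arms would read too high. Under the design alternative the enalapril arm, which has more deaths, would be raised more.

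**Working it through.** **Inputs from SAP 2.11 and 1.1**
- Enalapril: "an annualized event rate of 0.20 for the composite of CV death or first HF hospitalization in the enalapril group".
- Sacubitril/valsartan: "an annualized event rate of 0.16 for the composite of CV death or first HF hospitalization in the sacubitril/valsartan group".
- HF hospitalisation share of first CV events: 66%, applied here to both arms and at all times.
- 450 participants per arm, uniform accrual over 18 months, follow-up of 18 to 36 months, no loss to follow-up.
- Non-CV death rate: not given. Base case 0; an assumed 2 per 100 patient-years is shown as a sensitivity case.

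**Reproducing the plan's event count.** With constant rate r and censoring uniform on 1.5 to 3 years, expected events per arm are 450 × {1 − [exp(−1.5r) − exp(−3r)]/(1.5r)}.
- Enalapril: 450 × 0.3600 = 162.0.
- Sacubitril/valsartan: 450 × 0.3006 = 135.3.
- Total 297.3 against the plan's 302, a difference of 1.6%.

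Reading 0.20 and 0.16 as one-year risks instead gives 321.5, which does not fit, so they are treated as hazards.

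**Cause-specific hazards**
- Enalapril: hospitalisation h = 0.66 × 0.20 = 0.132; CV death first c = 0.34 × 0.20 = 0.068.
- Sacubitril/valsartan: h = 0.66 × 0.16 = 0.1056; c = 0.34 × 0.16 = 0.0544.

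**Formulas**
- One minus Kaplan-Meier targets 1 − exp(−ht).
- Cumulative incidence is h/(h+c) × {1 − exp(−(h+c)t)}.
- The SE of the Kaplan-Meier estimate is Greenwood's: exp(−ht) × √{∫ from 0 to t of h/[450 · exp(−(h+c)s) · G(s)] ds}, with G(s) = 1 up to 1.5 years and (3 − s)/1.5 after that.

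Example, enalapril at 30 months: 1 − exp(−0.33) = 28.1%, against 0.66 × (1 − exp(−0.5)) = 26.0%.

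| Arm | Months | 1−KM | Cumulative incidence | Excess (points) | SE (points) | Excess/SE |
|---|---|---|---|---|---|---|
| Enalapril | 12 | 12.37% | 11.96% | 0.4 | 1.58 | 0.25 |
| Enalapril | 18 | 17.96% | 17.11% | 0.9 | 1.86 | 0.46 |
| Enalapril | 24 | 23.20% | 21.76% | 1.4 | 2.13 | 0.68 |
| Enalapril | 30 | 28.11% | 25.97% | 2.1 | 2.54 | 0.84 |
| Sac/val | 12 | 10.02% | 9.76% | 0.3 | 1.44 | 0.18 |
| Sac/val | 18 | 14.65% | 14.08% | 0.6 | 1.70 | 0.33 |
| Sac/val | 24 | 19.04% | 18.07% | 1.0 | 1.96 | 0.49 |
| Sac/val | 30 | 23.20% | 21.76% | 1.4 | 2.35 | 0.61 |

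A simulation of 4,000 arms agrees: enalapril excess 1.43 points (0.68 SE) at 24 months and 2.06 points (0.82 SE) at 30 months.

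**Between-arm difference**
- 24 months: 4.16 points from Kaplan-Meier, 3.68 from cumulative incidence. Bias 0.48; SE of the difference √(2.13² + 1.96²) = 2.89; ratio 0.17.
- 30 months: 4.90 against 4.21. Bias 0.69; SE √(2.54² + 2.35²) = 3.46; ratio 0.20.

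**Sensitivity**
- Assumed non-CV death of 0.02 per year, enalapril, 30 months: cumulative incidence is (0.132/0.22) × (1 − exp(−0.55)) = 25.4%. The excess is 2.7 points, or 1.06 SE.
- HF hospitalisation share between 50% and 75% instead of 66%, enalapril, 24 months: the excess runs from 1.6 down to 1.2 points.

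**The case against.** The strongest reply is that no planned inference is biased. Neither document asks for an HF hospitalisation risk at a fixed time or for a risk difference; the curve accompanies a Cox model whose hazard ratio is valid as a cause-specific one. Death is also handled elsewhere: the win ratio ranks CV death above hospitalisation, the composite of the two has its own curve, and SAP 2.6.2.4 adds a joint frailty model. All of this stands and limits the harm. None of it changes what the HF hospitalisation curve shows.

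Four stronger readings are tempting, and the documents do not support them.

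- **That these curves are the only absolute-risk display.** Protocol 12.4.2 also plans counts and percentages of CV events by type, by arm, in the FAS and PPS, and SAP section 3 does not list that as dropped. With follow-up of 18 to 36 months, crude percentages cannot give risk at a fixed time, but they do show the observed share.
- **That the treatment contrast is materially inflated.** A difference of 4.9 instead of 4.2 points is about 16% too large in relative terms, but only one fifth of its SE.
- **That the error reaches 3 points or a full SE at the plan's rates.** It is 2.9 points in the enalapril arm at 36 months, when almost nobody is still at risk. Passing 1 SE requires a non-CV death rate that the documents do not give.
- **That the sudden-death curve is distorted as much.** No rates are given for it. At assumed rates of 0.03 to 0.04 per year for the event and 0.05 to 0.08 for other death, under the plan's censoring, the ratio peaks at about 0.3 to 0.5 SE.

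**Conclusion.** The point holds as a descriptive one. Followed as written, the plan produces HF hospitalisation curves that read too high in both arms. The excess is small in the first 18 months and reaches 0.84 SE (enalapril) and 0.61 SE (sacubitril/valsartan) by 30 months.

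These sizes rest on constant hazards, the planning rates, the 66% share applied equally to both arms, and no non-CV death. Higher mortality would enlarge them. The same issue applies in principle to CV death and to sudden death or resuscitated arrest, but the documents give no rates from which to size it there.

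The primary test and its error rate, the sample size, the hazard ratios and the composite endpoint are not in question. The change is worth making because it is cheap and the curves invite exactly the reading they cannot support.

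**What to change.** In SAP 2.5.3 and 2.6.2.1, present Aalen-Johansen cumulative incidence curves by arm for:

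- first HF hospitalisation, with death from any cause as the competing event;
- CV death, with non-CV death competing;
- sudden death or resuscitated arrest, with other death competing.

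State that any absolute risk or risk difference for these endpoints is taken from those curves. Keep the Cox models and label their hazard ratios cause-specific. Keep Kaplan-Meier for all-cause mortality, where nothing competes.

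The cost is a few sentences of SAP text and a small amount of R programming, with no new data and no change to any test. The displayed risks will be slightly lower.
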